Appendix 1: Schedule of Activities

ACQ-5=Asthma Control Questionnaire (5 items); ADA=anti-drug antibody; eDiary=electronic diary; EOT=end of treatment; ET=early termination; FeNO=fractional exhaled nitric oxide; PBO=placebo; PEFR=peak expiratory flow rate; PK=pharmacokinetic; PPD=purified protein derivative; Rand.=randomization; SNP=single nucleotide polymorphism; TB=tuberculosis; UV=unscheduled visit; WGS=whole genome sequencing.

Notes: On treatment days, all assessments should be performed prior to study drug dosing, unless otherwise specified.

- ^a The screening period may last up to 4 weeks. The earliest a patient can qualify for the run-in period is after 12 days, when eDiary compliance criteria are met. Patients are allowed one attempt to re-screen.
- ^b Run-in takes place from Day 1 through Day 14 to assess baseline eDiary symptoms; however, these assessments must be performed on Day 1 (± 2 days).
- ^c Note that these tests occur on the same day, before (left column) or after (right column) the patient has been randomized.
- ^d Patients who complete the treatment period will return to the clinic for a treatment completion visit at Week 50. Patients who discontinue study drug for any reason should continue follow-up for all remaining study visits through the end of the study.
- ^e Final safety follow-up will be conducted by telephone call.
- ^f Patients who experience symptoms consistent with an asthma exacerbation will be asked to come to the clinic for an unscheduled visit for additional evaluations. Assessments should be performed as clinically indicated.
- ^g Patients who are randomly allocated to the 48-week double-blind treatment period but discontinue study drug should continue follow-up for all other study procedures and measurements through the end of the study, except for collection of serum and nasosorption samples for biomarkers.
- ^h Informed consent must be documented before any study-specific screening procedure is performed.
- ⁱ Includes evaluation of the head, eyes, ears, nose, and throat, and the cardiovascular, dermatologic, musculoskeletal, respiratory, gastrointestinal, and neurologic systems.
- ^j Limited, symptom-directed physical examinations should be performed at specified visits during the placebo-controlled period and as clinically indicated. The examination should include, at a minimum, evaluation of the heart, lungs, and appropriate evaluations based on reported adverse events or symptoms. At the time of each follow-up limited physical examination, an interval medical history should be obtained and any changes in medications and allergies should be recorded.
- ^k eDiary compliance must be demonstrated on 5 of 7 days during each of the 2 consecutive weeks of the run-in period. eDiary compliance less than 70% (fewer than 5 out of 7 days/week) during the run-in period will result in study discontinuation. Patients must meet additional eligibility criteria for the double-blind treatment period as outlined in Section [4.1.1.2](#).
- ^l Includes respiratory rate, pulse rate, systolic and diastolic blood pressure while the patient is in a seated position (resting for at least 5 minutes), and temperature.

Appendix 1: Schedule of Activities

- ^m Vital signs and a focused physical examination (e.g., for signs of hypersensitivity reaction) will be monitored serially (every 15 [\pm 3] minutes) during both study drug administration and for the first hour immediately after dosing. Thereafter, vital signs and a focused physical examination will be performed every hour (\pm 10 minutes) ending at the investigator's discretion.
- ⁿ Concomitant therapy consists of any medication (e.g., prescription drugs, over-the-counter drugs, vaccines, herbal or homeopathic remedies, nutritional supplements) used by a patient in addition to protocol-mandated treatment from 7 days prior to screening (for medications not intended for the treatment of asthma) or 3 months prior to screening (for medications intended for the treatment of asthma) to the study completion/discontinuation visit.
- ^o Urine drug screen includes, but is not limited to, amphetamines, barbiturates, benzodiazepines, cocaine, cotinine, marijuana/cannabinoids (tetrahydrocannabinol), methadone, methamphetamines, methylenedioxymethamphetamine, opiates, and phencyclidine.
- ^p Hematology includes WBC count, RBC count, hemoglobin, hematocrit, platelet count, and differential count (neutrophils, eosinophils, basophils, monocytes, lymphocytes, other cells).
- ^q Only to be performed after the patient is randomized.
- ^r Chemistry panel (serum or plasma) includes sodium, potassium, chloride, bicarbonate or total carbon dioxide (if considered standard of care for the region), glucose, BUN or urea, creatinine, calcium, magnesium, phosphate, total protein, albumin, total and direct bilirubin, ALP, ALT, AST, urate, LDH, creatinine kinase, and hemoglobin A1c.
- ^s Urinalysis includes dipstick (pH, specific gravity, glucose, protein, ketones, bilirubin, nitrite, blood) and microscopic examination (sediment, RBCs, WBCs, casts, crystals, epithelial cells, bacteria). If urinalysis is abnormal, reflex testing for culture and antibiotic sensitivity should be performed if clinically indicated.
- ^t All women of childbearing potential will have a serum pregnancy test at screening. Urine pregnancy tests will be performed at specified subsequent visits. If a urine pregnancy test is positive, dosing should be held and a serum pregnancy test performed for confirmation.
- ^u Patients who are not eligible for randomization into the double-blind treatment period should be discontinued from the study. They are not eligible for re-screening. In addition, these patients should be informed that the first dose given at run-in was a placebo and, therefore, there is no additional requirement for follow-up visits.
- ^v Includes hepatitis B surface antibody, hepatitis B surface antigen, total hepatitis B core antibody, hepatitis B DNA (if hepatitis B surface antigen test is negative and total hepatitis B core antibody test is positive), hepatitis C virus antibody, hepatitis C virus RNA (if hepatitis C virus antibody test is positive), and HIV1/2 antibody.
- ^w Patients with a positive PPD test or a QuantiFERON[®] TB Gold test that is positive or indeterminate will require a chest X-ray to review for evidence of active TB as described in Section 4.5.11.
- ^x Refer to Section 4.5.6 for FeNO procedure restrictions.

Appendix 1: Schedule of Activities

- ^y Prohibited medication use prior to spirometry is described in Section 4.4.4. If the patient has used a bronchodilator within the time window defined in Section 4.4.4, then the visit must be rescheduled. To accommodate the rescheduled visit, the usual visit window during the treatment period may be extended to \pm 4 days for Week 2, \pm 5 days for Week 3, and \pm 6 days for all other visits.
- ^z Patients will use an eDiary to record asthma symptoms, PEFR, and use of short-acting rescue therapy twice daily prior to taking asthma controller medications. Refer to Section 4.5.8 for compliance requirements. The eDiary will remind patients twice daily to complete their entries and will provide a time window during which the entry must be completed at approximately the same time each day. On the days of study visits, if the patient has not performed the morning PEFR measurement before arrival at the clinic, the PEFR should be measured at the clinic (see Section 4.5.8.2).
- ^{aa} On all study drug administration days that require PK serum sampling, PK samples will be obtained pre-dose and post-dose (2 hours \pm 30 minutes *after the end of the dose*). On clinic visit days where study drug is not administered and PK serum sampling is required, only one PK sample is to be obtained.
- ^{bb} To be collected predose.
- ^{cc} Samples will also be used for PK and biomarker analyses.
- ^{dd} Not applicable for a site that has not been granted approval for WGS.
- ^{ee} After informed consent has been obtained but prior to initiation of study drug, only serious adverse events caused by a protocol-mandated intervention should be reported. After initiation of study drug, all adverse events will be reported until 84 days after the final dose of study drug or end of study (Week 58) for patients who discontinue study drug but remain on study, whichever occurs later, or 6 weeks following the placebo dose for patients who failed to be randomized. After this period, the Sponsor should be notified if the investigator becomes aware of any serious adverse event that is believed to be related to prior study drug treatment (see Section 5.6).
- ^{ff} Patients should be administered the study drug over 1 hour, and observed for 1 hour post-infusion, with observation ending at the investigator's discretion (as described in footnote "m").

Appendix 2
Asthma Control Questionnaire, 5-Item Version

**ASTHMA CONTROL
QUESTIONNAIRE (ACQ)**

© 1997

Appendix 2: Asthma Control Questionnaire, 5-Item Version

ASTHMA CONTROL QUESTIONNAIRE®

PATIENT ID: _____

DATE: _____

Page 1 of 2

Please answer questions 1 - 6.

Circle the number of the response that best describes how you have been during the past week.

1. On average, during the past week, how often were you woken by your asthma during the night?
0 Never
1 Hardly ever
2 A few times
3 Several times
4 Many times
5 A great many times
6 Unable to sleep because of asthma

2. On average, during the past week, how bad were your asthma symptoms when you woke up in the morning?
0 No symptoms
1 Very mild symptoms
2 Mild symptoms
3 Moderate symptoms
4 Quite severe symptoms
5 Severe symptoms
6 Very severe symptoms

3. In general, during the past week, how limited were you in your activities because of your asthma?
0 Not limited at all
1 Very slightly limited
2 Slightly limited
3 Moderately limited
4 Very limited
5 Extremely limited
6 Totally limited

4. In general, during the past week, how much shortness of breath did you experience because of your asthma?
0 None
1 A very little
2 A little
3 A moderate amount
4 Quite a lot
5 A great deal
6 A very great deal

Revised September 2010
ACQ-SA North American English Version

Appendix 2: Asthma Control Questionnaire, 5-Item Version

ASTHMA CONTROL QUESTIONNAIRE®

PATIENT ID: _____

DATE: _____

Page 2 of 2

5. In general, during the past week, how much of the time did you wheeze?

0	Not at all
1	Hardly any of the time
2	A little of the time
3	A moderate amount of the time
4	A lot of the time
5	Most of the time
6	All the time

Appendix 3

Tuberculosis Worksheet

Patient: _____

Visit: 1 (Screening)

Person completing form: _____

Date: _____

Patient must have either a purified protein derivative (PPD) or QuantiFERON TB Gold test per exclusion criteria in protocol Section 4.1.2. Please answer the following for potential patients **per the information recorded in the source document**.

1.1 Does the patient have active tuberculosis?

- No. Continue to 2.1.
- Yes. **Stop** – this patient must be excluded from the study.

2.1 If the patient had a PPD test, is the result negative (< 5 mm induration at 48 to 72 hours after the test was placed) or positive (≥ 5 mm induration at 48 to 72 hours after the test was placed)?

- Negative. Patient is eligible per exclusion criterion in protocol Section 4.1.2.
- Positive. Continue to 2.2.
- N/A. Patient had QuantiFERON TB Gold test instead of a PPD. Continue to 2.3.

2.2 Does patient have a history of bacille Calmette-Guérin (BCG) vaccination?

- Yes. Patient should have a QuantiFERON TB Gold test performed. After QuantiFERON results are available, continue to 2.3.
- No/Unknown. Continue to 3.1.

2.3 What is the result of the QuantiFERON TB Gold test?

- Negative. Patient is eligible per exclusion criterion in protocol Section 4.1.2.
- Indeterminate or Positive. Continue to 3.1.

3.1 Does the patient currently have any of the following symptoms?

- Productive, prolonged cough (>3 weeks)
- Coughing up blood
- Fever
- Night sweats
- Unexplained appetite loss
- Unintentional weight loss

- No. Continue to 3.2.
- Yes. **Stop** – this patient must be excluded from the study.

Person assessing item 3.1

Signature

Date

3.2 Does the patient have a documented history of adequate prophylaxis (**completed course** for latent tuberculosis per the treatment options as stated in the WHO guidelines; WHO 2018)?

- Yes. Continue to 3.3.

Appendix 3: Tuberculosis Worksheet

No. **Stop** – this patient must be excluded from the study.

3.3 Has the patient had any known exposure to a case of active tuberculosis since their most recent prophylaxis?

Yes. **Stop** – the patient must be excluded from the study.
 No. Continue to 3.4.

3.4 Has the patient had a chest radiograph or CT scan within 3 months prior to screening?

No. A chest radiograph should be performed per protocol Section [4.5.12](#), and continue to 3.5.
 Yes. Continue to 3.5.

3.5 Is there evidence of active tuberculosis on the chest radiograph or CT?

No. Patient is eligible per exclusion criterion in protocol Section [4.1.2](#).
 Yes. **Stop** – this patient must be excluded from the study.

Appendix 4

Daytime eDiary

Please answer the following questions first thing in the morning. These questions ask about your asthma after you went to sleep last night.

1. How severe were your asthma symptoms after going to sleep last night (shortness of breath, cough, wheeze, or chest tightness)?

- I had no asthma symptoms after going to sleep last night
- Mild
- Moderate
- Severe
- Very Severe

2. After going to sleep last night, did you wake up because of your asthma symptoms (shortness of breath, cough, wheeze, or chest tightness)?

- No
- Yes

3. After going to sleep last night, did you take any rescue medication for your asthma symptoms (shortness of breath, cough, wheeze, or chest tightness)?

- No, I did not take any rescue medication
- Yes, I used a rescue inhaler

How many puffs of a rescue inhaler did you take? _____ puffs

- Yes, I used a nebulizer (breathing machine)

How many times did you use a nebulizer (breathing machine)?
_____ times

Appendix 5 Nighttime eDiary

Please answer the following questions in the evening, just before bedtime. These questions ask about your asthma today, from waking up until now.

1. How severe were your asthma symptoms today (shortness of breath, cough, wheeze, or chest tightness)?

- I had no asthma symptoms today
- Mild
- Moderate
- Severe
- Very Severe

2. Did you take any rescue medication for your asthma symptoms today (shortness of breath, cough, wheeze, or chest tightness)?

- No, I did not take any rescue medication
- Yes, I used a rescue inhaler

How many puffs of a rescue inhaler did you take? _____ puffs

- Yes, I used a nebulizer (breathing machine)

How many times did you use a nebulizer (breathing machine)?
_____ times

Appendix 6 **Anaphylaxis Precautions and Diagnosis**

Anaphylaxis Precautions

These guidelines are intended as a reference and should not supersede pertinent local or institutional standard operating procedures.

The following equipment is needed in the event of a suspected anaphylactic reaction during study drug infusion:

- Monitoring devices: ECG monitor, blood pressure monitor, oxygen saturation monitor, and thermometer
- Oxygen
- Epinephrine for intravenous, intramuscular, and endotracheal administration in accordance with institutional guidelines
- Antihistamines
- Corticosteroids
- Intravenous infusion solutions, tubing, catheters, and tape

The following are the procedures to follow in the event of a suspected anaphylactic reaction during study drug infusion:

- Stop the study drug infusion.
- Call for additional medical assistance.
- Maintain an adequate airway.
- Ensure that appropriate monitoring is in place, with continuous ECG and pulse oximetry monitoring, if possible.
- Administer antihistamines, epinephrine, or other medications as required by patient status and as directed by the physician in charge.
- Continue to observe the patient and document observations.
- Draw serum/plasma samples for immunogenicity testing.
- Ask patient to return for washout immunogenicity sample if appropriate.

Appendix 6: Anaphylaxis Precautions and Diagnosis

Criteria for Anaphylaxis Diagnosis

Anaphylaxis is highly likely when any one of the following criteria are fulfilled (adapted from Sampson et al. 2006):

1. Acute onset of an illness (minutes to several hours) with involvement of the skin, mucosal tissue, or both (e.g., generalized hives, pruritis or flushing, swollen lips-tongue-uvula)

AND AT LEAST ONE OF THE FOLLOWING:

- a. Respiratory compromise (e.g., dyspnea, wheeze-bronchospasm, stridor, reduced PEF, hypoxemia)
 - b. Reduced BP or associated symptoms of end-organ dysfunction (e.g., hypotonia [collapse], syncope, incontinence)
2. Two or more of the following that occur rapidly after exposure to a likely allergen for that patient (minutes to several hours):
 - a. Involvement of the skin-mucosal tissue (e.g., generalized hives, itch-flush, swollen lips-tongue-uvula)
 - b. Respiratory compromise (e.g., dyspnea, wheeze-bronchospasm, stridor, reduced PEF, hypoxemia)
 - c. Reduced BP or associated symptoms (e.g., hypotonia [collapse], syncope, incontinence)
 - d. Persistent gastrointestinal symptoms (e.g., crampy, abdominal pain, vomiting)

Reference:

Appendix 7

WHO Toxicity Grading Scale

ITEM	Grade 1 Toxicity	Grade 2 Toxicity	Grade 3 Toxicity	Grade 4 Toxicity
HEMATOLOGY				
Hemoglobin	9.5–10.5 g/dL	8.0–9.4 g/dL	6.5–7.9 g/dL	< 6.5 g/dL
Absolute neutrophil count	1000–1500/mm ³	750–999/mm ³	500–749/mm ³	<500/mm ³
Platelets	75,000–99,000/mm ³	50,000–74,999/mm ³	20,000–49,000/mm ³	<20,000/mm ³
PT	1.01–1.25×ULN	1.26–1.5×ULN	1.51–3.0×ULN	>3×ULN
aPPT	1.01–1.66×ULN	1.67–2.33×ULN	2.34–3×ULN	> 3×ULN
Fibrinogen	0.75–0.99×LLN	0.50–0.74×LLN	0.25–0.49×LLN	< 0.25×LLN
Fibrin split product	20–40 µg/mL	41–50 µg/mL	51–60 µg/mL	> 60 µg/mL
Methemoglobin	5%–9.9%	10.0%–14.9%	15.0%–19.9%	> 20%
LIVER ENZYMES				
AST (SGOT)	1.25–2.5×ULN	2.6–5×ULN	5.1–10×ULN	> 10×ULN
ALT (SGPT)	1.25–2.5×ULN	2.6–5×ULN	5.1–10×ULN	> 10×ULN
GGT	1.25–2.5×ULN	2.6–5×ULN	5.1–10×ULN	> 10×ULN
ALP	1.25–2.5×ULN	2.6–5×ULN	5.1–10×ULN	> 10×ULN
Amylase	1.1–1.5×ULN	1.6–2.0×ULN	2.1–5.0×ULN	> 5.1×ULN
CHEMISTRIES				
Hyponatremia	130–135 mEq/L	123–129 mEq/L	116–122 mEq/L	< 116 or mental status changes or seizures
Hypernatremia	146–150 mEq/L	151–157 mEq/L	158–165 mEq/L	> 165 mEq/L or mental status changes or seizures
Hypokalemia	3.0–3.4 mEq/L	2.5–2.9 mEq/L	2.0–2.4 mEq/L or intensive replacement Rx required or hospitalization required	< 2.0 mEq/L or paresis or ileus or lifethreatening arrhythmia
Hyperkalemia	5.6–6.0 mEq/L	6.1–6.5 mEq/L	6.6–7.0 mEq/L	> 7.0 mEq/L or lifethreatening arrhythmia
Hypoglycemia	55–64 mg/dL	40–54 mg/dL	30–39 mg/dL	<30 mg/dL or mental status changes or coma
Hyperglycemia (note if fasting)			251–500 mg/dL	> 500 mg/dL or ketoacidosis or seizures

Appendix 7: WHO Toxicity Grading Scale

ITEM	Grade 1 Toxicity	Grade 2 Toxicity	Grade 3 Toxicity	Grade 4 Toxicity
Hypocalcemia (corrected for albumin)	8.4–7.8 mg/dL	7.7–7.0 mg/dL	6.9–6.1 mg/dL	< 6.1 mg/dL or lifethreatening arrhythmia or tetany
Hypercalcemia (correct for albumin)	10.6–11.5 mg/dL	11.6–12.5 mg/dL	12.6–13.5 mg/dL	> 13.5 mg/dL lifethreatening arrhythmia
Hypomagnesemia	1.4–1.2 mEq/L	1.1–0.9 mEq/L	0.8–0.6 mEq/L	< 0.6 mEq/L or lifethreatening arrhythmia
Hypophosphatemia	2.0–2.4 mg/dL	1.5–1.9 mg/dL or replacement Rx required	1.0–1.4 mg/dL intensive Rx or hospitalization required	< 1.0 mg/dL or lifethreatening arrhythmia
Hyperbilirubinemia	1.1–1.5×ULN	1.6–2.5×ULN	2.6–5×ULN	> 5×ULN
BUN	1.25–2.5×ULN	2.6–5×ULN	5.1–10×ULN	> 10×ULN
Creatinine	1.1×1.5×ULN	1.6–3.0×ULN	3.1–6×ULN	> 6×ULN or required dialysis
URINALYSIS				
Proteinuria	1+ or < 0.3% or <3 g/L or 200 mg–1 g loss/day	2–3+ or 0.3%–1.0% or 3–10 g/L or 1–2 g loss/day	4+ or > 1.0% or > 10 g/L or 2–3.5 g loss/day	nephrotic syndrome or > 3.5 g loss/day
Hematuria	Microscopic only	Gross, no clots	Gross+ clots	Obstructive or required transfusion
CARDIAC DYSFUNCTION				
Cardiac rhythm		Asymptomatic, transient signs, no Rx required	Recurrent/persistent; no Rx required	Requires treatment
Hypertension	Transient inc. > 20 mm; no Rx	Recurrent, chronic, > 20 mm, Rx required	Requires acute Rx; no hospitalization	Requires hospitalization
Hypotension	Transient orthostatic hypotension, no Rx	Symptoms correctable with oral fluids Rx	Requires IV fluids; no hospitalization required	Requires hospitalization
Pericarditis	Minimal effusion	Mild/moderate asymptomatic effusion, no Rx	Symptomatic effusion; pain; EKG changes	Tamponade; pericardiocentesis or surgery required

Appendix 7: WHO Toxicity Grading Scale

ITEM	Grade 1 Toxicity	Grade 2 Toxicity	Grade 3 Toxicity	Grade 4 Toxicity
Hemorrhage, blood loss	Microscopic/occult	Mild, no transfusion	Gross blood loss; 1–2 units transfused	Massive blood loss; > 3 units transfused
RESPIRATORY				
Cough	Transient; no Rx	Treatment associated cough; local Rx	Uncontrolled	
Bronchospasm, acute	Transient; no Rx < 80%–70% FEV ₁ (or peak flow)	Requires Rx normalizes with bronchodilator; FEV ₁ 50%–70% (or peak flow)	No normalization with bronchodilator; FEV ₁ 25%–50% (or peak flow retractions)	Cyanosis: FEV ₁ < 25% (or peak flow) or intubated
GASTROINTESTINAL				
Stomatitis	Mild discomfort; no limits on activity	Some limits on eating/drinking	Eating/talking very limited	Requires IV fluids
Nausea	Mild discomfort; maintains reasonable intake	Moderate discomfort; intake decreased significantly; some activity limited	Severe discomfort; no significant intake; activities limited	Minimal fluid intake
Vomiting	Transient emesis	Occasional/moderate vomiting	Orthostatic hypotension or IV fluids required	Hypotensive shock or hospitalization required for IV fluid therapy
Constipation	Mild	Moderate	Severe	Distensions with vomiting
Diarrhea	Transient 3–4 loose stools/day	5–7 loose stools/day	Orthostatic hypotension or > 7 loose stools/day or required IV fluids	Hypotensive shock or hospitalization for IV fluid therapy required
NEURO & NEUROMUSCULAR				
Neuro–cerebellar	Slight incoordination dysdiadochokinesis	Intention tremor, dysmetria, slurred speech; nystagmus	Locomotor ataxia	Incapacitated
Mood	Mild anxiety or depression	Moderate anxiety or depression and therapy required	Severe anxiety or depression or mania; needs assistance	Acute psychosis; incapacitated, requires hospitalization

Appendix 7: WHO Toxicity Grading Scale

ITEM	Grade 1 Toxicity	Grade 2 Toxicity	Grade 3 Toxicity	Grade 4 Toxicity
Neuro control	Mild difficulty concentrating; no Rx; mild confusion/agitation; ADL unaffected	Moderate confusion/agitation some limitation of ADL; minimal Rx	Severe confusion/agitation needs assistance for ADL; therapy required	Toxic psychosis; hospitalization
Muscle strength	Subjective weakness; no objective symptoms/signs	Mild objective signs/symptoms; no decrease in function	Objective weakness function limited	Paralysis
OTHER PARAMETERS				
Fever: oral, > 12 hours	37.7°C –38.5°C or 100.0°F –101.5°F	38.6°C –39.5°C or 101.6°F –102.9°F	39.6°C –40.5°C or 103°F –105°F	> 40°C or > 105°F
Headache	Mild, no Rx therapy	Transient, moderate; Rx required	Severe; responds to initial narcotic therapy	Intractable; required repeated narcotic therapy
Fatigue	No decrease in ADL	Normal activity decreased 25%–50%	Normal activity decreased > 50% can't work	Unable to care for self
Allergic reaction	Pruritus without rash	Localized urticaria	Generalized urticaria; angioedema	Anaphylaxis
Local reaction	Tenderness or erythema	Induration < 10 cm or phlebitis or inflammation	Induration > 10 cm or ulceration	Necrosis
Mucocutaneous	Erythema; pruritus	Diffuse, maculopapular rash, dry desquamation	Vesiculation, moist desquamation, or ulceration	Exfoliative dermatitis, mucous membrane involvement or erythema, multiforme or suspected StevensJohnson or necrosis requiring surgery

ADL=activities of daily living; FEV₁=forced expiratory volume in 1 second; LLN=lower limit of normal; Rx=treatment; ULN=upper limit of normal.

Appendix 8

Detailed Definition of Diary Worsening Events

Diary events are based on objective measures of deterioration of peak expiratory flow rate (PEFR), rescue therapy use, and asthma symptoms assessed morning and evening (overall, six parameters) recorded twice-daily in an eDiary. Deterioration is defined as either reaching a predefined change from baseline (threshold), for at least 2 consecutive days, or deterioration in all six parameters over a 5-day period plus at least one parameter reaching a threshold criterion for 2 consecutive days. Seven deteriorating criteria are used to construct the diary events. Deterioration of at least two concurrent criteria is needed to fulfill the criteria for a diary event. The light grey cells represent the 14 different two-criteria diary event combinations.

	Threshold				
	Minimum change from baseline in PEFR (%), rescue therapy use (doses), and asthma symptoms score, morning or evening, for at least 2 consecutive days				Slope
	Rescue therapy: 1.5× increase from baseline		Symptom score: Increase of 1 from baseline or absolute maximum score		Deterioration over 5 days in all six parameters
	morning	evening	morning	evening	
PEFR, morning 15% reduction from baseline					
PEFR, evening 15% reduction from baseline					
Rescue therapy, morning 1.5 × increase from baseline					
Rescue therapy, evening 1.5 × increase from baseline					
Symptom score, morning Increase of 1 from baseline or absolute maximum score					
Symptom score, evening Increase of 1 from baseline or absolute maximum score

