4.6 TREATMENT, PATIENT, STUDY, AND SITE DISCONTINUATION

4.6.1 Study Treatment Discontinuation

Patients must permanently discontinue study treatment if they experience any of the following:

- Any medical condition that the investigator or Sponsor determines may jeopardize the patient's safety if he or she continues to receive study treatment
- Any Grade 4 adverse event that the investigator or Sponsor determines to be related to study treatment. This excludes asthma exacerbations, unless they meet one of the other criteria for study treatment discontinuation.

- Investigator or Sponsor determination that treatment discontinuation is in the best interest of the patient
- Pregnancy
- Suspicion of hypersensitivity or anaphylactic reaction to study drug (i.e., generalized urticaria or angioedema [WHO Grade 3 allergic reaction] or anaphylaxis [Grade 4 allergic reaction] related to study drug, or Grade 3 or 4 infusion related reaction)

The primary reason for study treatment discontinuation should be documented on the appropriate eCRF. Patients who discontinue study treatment prematurely will not be replaced and should continue follow-up for all other study procedures and measurements through the end of the study (Week 58).

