5.1.1.3 Infusion-Related Reactions

In patients who receive study drug intravenously, infusion-related reactions may occur. These may be acute—often overlapping in symptoms with a hypersensitivity or anaphylactic reaction. Should such an acute reaction take place, the patient should be managed following the scheme as for anaphylaxis (see [Appendix 6](#)). Infusion-related reactions may also be delayed, occurring hours to days (up to 14 days) after administration. These delayed symptoms are frequently similar to those of serum sickness: rash, vasculitis, erythema multiforme, Stevens-Johnson syndrome, and toxic epidermal necrolysis (Corominas et al. 2014). If a delayed infusion-related reaction is suspected, the patient should discontinue study drug, and appropriate clinical management should be applied.

In the Phase I clinical study in healthy volunteers, no subjects have had any infusion-related reactions.

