5.1.2 Management of Patients Who Experience Adverse Events

5.1.2.1 Treatment Interruption

Reduction in dosing for adverse events is not permitted. Patients who experience certain adverse events considered to be related to study drug should be discontinued from treatment as described in Section 4.6.1.

Study treatment may be temporarily suspended in patients who experience toxicity considered to be related to study drug. If study treatment has been withheld for two or more consecutive dosing visits because of toxicity, the patient should be discontinued from study treatment. However, if the adverse event(s) that led to withholding dosing shows clear evidence of improvement, treatment may be resumed following discussion with and approval by the Medical Monitor. Study treatment may be suspended for reasons other than toxicity (e.g., surgical procedures), but must be approved by the Medical Monitor. The investigator and the Medical Monitor will determine an acceptable length of time for the treatment interruption.

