5.3.3 Assessment of Severity of Adverse Events

The WHO Toxicity Grading Scale (see [Appendix 7](#)) will be used for assessing adverse event severity. [Table 3](#) will be used for assessing severity for adverse events that are not specifically listed in the WHO Toxicity Grading Scale.

Table 3 Adverse Event Severity Grading Scale for Events Not Specifically Listed in WHO Toxicity Grading Scale

Grade	Severity
1	Mild; transient or mild discomfort (<48 hours); no medical intervention or therapy required
2	Moderate; mild to moderate limitation in activity; some assistance may be needed; no or minimal medical intervention or therapy required
3	Severe; marked limitation in activity; some assistance usually required; medical intervention or therapy required; hospitalization possible
4	Life-threatening; extreme limitation in activity; significant assistance required; significant medical intervention or therapy required, hospitalization or hospice care probable

Notes: Developed by the Division of Microbiology and Infectious Diseases.

Regardless of severity, some events may also meet seriousness criteria. Refer to definition of a serious adverse event (see Section [5.2.2](#)).

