5.3.5.1 Infusion-Related or Injection Reactions

Adverse events that occur during or within 24 hours after study drug administration should be captured as individual signs and symptoms on the Adverse Event eCRF rather than an overall diagnosis (e.g., record dyspnea and hypotension as separate events rather than a diagnosis of infusion-related or anaphylactic reaction).

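### Appendix 7 fever row: Grade 3 runs to 40.5 °C but Grade 4 starts above 40 °C, so 40.1–40.5 °C meets both grades by the Celsius limits, with no tie-break

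*Protocol*

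**What the plan says.** The fever row of Protocol Appendix 7 applies to oral temperature raised for more than 12 hours. Its Grade 3 cell reads "39.6°C –40.5°C or 103°F –105°F". The Grade 4 cell beside it covers anything above 40 °C or above 105 °F.

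Section 5.3.3 makes this the working scale: Appendix 7 "will be used for assessing adverse event severity". The grade has a dosing consequence. Section 4.6.1 requires permanent discontinuation for "Any Grade 4 adverse event that the investigator or Sponsor determines to be related to study treatment", asthma exacerbations generally excepted.

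Other rules also bear on a febrile patient:
- Section 4.6.1 requires a stop on "Investigator or Sponsor determination that treatment discontinuation is in the best interest of the patient", and its hypersensitivity item ends with "or Grade 3 or 4 infusion related reaction".
- Section 5.1.2.1: "Study treatment may be temporarily suspended in patients who experience toxicity considered to be related to study drug".
- Section 5.1.1.3: "If a delayed infusion-related reaction is suspected, the patient should discontinue study drug".
- Section 5.3.5.1: events during an infusion or in the 24 hours after it "should be captured as individual signs and symptoms on the Adverse Event eCRF rather than an overall diagnosis".

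SAP Output 4.14 tabulates adverse events by highest WHO grade, with one line for Grade 3, one for Grade 4 and one for the two combined.

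**The concern.** Adjacent grades of a severity scale should not share readings, and limits given in two units should describe the same temperature. This boundary fails on both counts. Two sites, or one site with two thermometers, could grade the same fever differently and both be following the appendix.

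For a fever judged related to study drug and not handled as an infusion-related reaction, the grade decides whether the patient falls under a mandatory permanent stop or under judgement-based rules. In reporting, the same fever can land on either of two lines of Output 4.14. Fever is a relevant sign for this product: Section 5.1.1.2 lists it among the features of systemic reactions to large-molecule drugs.

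**Working it through.** **Inputs.** All limits come from the Appendix 7 fever row. Conversion: °F = 1.8 × °C + 32.

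**Step 1: do the printed units agree?**

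| Limit | Printed °C | Converted to °F | Printed °F | Gap (°F) |
|---|---|---|---|---|
| Grade 1 lower | 37.7 | 99.86 | 100.0 | 0.14 |
| Grade 1 upper | 38.5 | 101.30 | 101.5 | 0.20 |
| Grade 2 lower | 38.6 | 101.48 | 101.6 | 0.12 |
| Grade 2 upper | 39.5 | 103.10 | 102.9 | 0.20 |
| Grade 3 lower | 39.6 | 103.28 | 103 | 0.28 |
| Grade 3 upper | 40.5 | 104.90 | 105 | 0.10 |
| Grade 4 (above) | 40 | 104.00 | 105 | 1.00 |

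Six pairs agree within 0.28 °F. The Grade 4 pair is off by 1.00 °F. In Celsius, (105 − 32) / 1.8 = 40.56, a gap of 0.56 °C.

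**Step 2: which readings are affected?** The Grade 3 Celsius range holds ten one-decimal readings, 39.6 to 40.5. Five of them are also above 40 °C: 40.1 (104.18 °F), 40.2 (104.36), 40.3 (104.54), 40.4 (104.72) and 40.5 (104.90). None of the five is above 105 °F. So by the Celsius limits they meet Grades 3 and 4, and by the Fahrenheit limits alone they meet Grade 3. Readings of 39.6–40.0 °C are Grade 3 in both units, and 40.6 °C (105.08 °F) is Grade 4 in both.

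On a Fahrenheit thermometer the Grade 3 range holds 21 one-decimal readings, 103.0 to 105.0. Ten of them, 104.1 (40.06 °C) to 105.0 (40.56 °C), convert to above the Grade 4 Celsius limit.

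**Step 3: is there a tie-break?** Three places might supply one, and none does.
- Table 3 in Section 5.3.3 covers only events missing from the WHO scale. Fever is listed.
- Section 5.3.5.4 asks for the most extreme severity when a persistent event worsens over time. It does not address a single reading that fits two grades.
- SAP Output 4.14 takes the highest of the grades already assigned. It does not assign them.

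**Step 4: smaller mismatches in the same row.** 37.7 °C is Grade 1, but its 99.86 °F is below the Grade 1 floor of 100.0. 38.6 °C is Grade 2, but 101.48 °F lies within Grade 1. 39.5 °C is Grade 2, but 103.10 °F lies within Grade 3.

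**Step 5: candidate limits.** Grade 4 above 40.5 °C or 105 °F leaves no one-decimal Celsius reading in two grades, and the units agree within 0.10 °F. One Fahrenheit reading, 105.0 °F (40.56 °C), would still depend on the unit. Grade 3 to 40.0 °C / 104 °F with Grade 4 above that gives exact agreement.

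**The case against.** The strongest reply is that Appendix 7 reproduces a named external scale and may do so faithfully. If so, the protocol has not made a drafting error. That stands as far as the cause goes. A reader might infer a transcription slip from the 1.00 °F gap, but the documents cannot show one. The origin does not settle which grade a site should assign.

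A reader might also infer that the word joining the units in the Grade 4 cell settles the matter, so that anything above 40 °C is Grade 4. It does not: the Grade 3 cell joins its units in the same way and expressly includes 40.1–40.5 °C. Nor is a Fahrenheit site clearly in Grade 3. That holds only if the Celsius alternative in the Grade 4 cell is ignored.

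The practical reach is narrow, and this objection largely stands. The fever must be oral, last more than 12 hours, fall in a band of about half a degree, be judged related, and not be handled as an infusion-related reaction. Infusion-related reactions already lead to a stop at Grade 3 or 4, or on suspicion if delayed, and a fever that is part of a known diagnosis is generally not graded separately (Section 5.3.5.2). Nor does a Grade 3 label mean that dosing continues, because the best-interest stop and the suspension rule still apply. Those rules rest on judgement, so they soften the inconsistency without removing it.

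Other rows have oddities too: amylase Grade 3 ends at 5.0 × ULN while Grade 4 starts above 5.1, and hemorrhage leaves exactly 3 transfused units ungraded. Those are gaps. The fever row is an overlap at a limit that can trigger a mandatory stop.

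**Conclusion.** The point holds as a minor defect in an operative table. An oral fever of 40.1–40.5 °C lasting more than 12 hours meets Grades 3 and 4 by the Celsius limits and Grade 3 only by the Fahrenheit limits read alone, and no text resolves it.

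Two things depend on it: whether the mandatory Grade 4 stop applies to a related fever outside the infusion-reaction rules, and how such fevers split between the Grade 3 and Grade 4 lines of Output 4.14. A fever within 24 hours of infusion is recorded as its own term, so its reported grade can shift even where a stop is already required.

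A reader might infer that the safety tables or the monitoring trigger are compromised. They are not. The combined Grade 3-4 line, the Grade 3+ version of Output 4.7 and the Internal Monitoring Committee trigger (Grade 3 or higher, Section 3.1.3) give the same answer under either grade. No efficacy result uses the scale.

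Possibly no patient is affected. Section 1.2 reports only Grade 1 or 2 events in 106 healthy volunteers, though that gives no rate for patients with asthma, and enrollment is closed at 134. The conclusion assumes that the Grade 4 Celsius figure is printed as 40 with no decimal, and it leaves the cause open.

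**What to change.** 1. Check the whole fever row against the source scale, then state one non-overlapping Grade 3/4 limit in both units. One option is Grade 4 above 40.5 °C or above 105 °F. The stricter one ends Grade 3 at 40.0 °C / 104 °F and starts Grade 4 above that. In the same edit, name one unit as governing, which settles the smaller mismatches at 37.7, 38.6 and 39.5 °C.
2. While any patient is still being dosed, tell sites to apply the higher grade in the overlap. The reason is caution only, since the printed wording does not favour either grade. The documents do not say whether dosing has ended. If it has, this step lapses.
3. Before Output 4.14 is run, check the grade of any recorded fever of 40.1–40.5 °C or 104.1–105.0 °F.

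The cost is one table row (one cell, or two for the stricter limit, plus the note on the governing unit), a short site clarification and a small data check. Because the limit feeds a mandatory-stop rule, the clarification may need IRB/EC approval and, as locally required, regulatory approval under Section 9.7.
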